### 3.3 Selection of Subjects

Selection of subjects will be completed by meeting the subject eligibility criteria listed in this section.

Inclusion Criteria (answer must be YES to all criteria listed below)

1. Patients must have histologically confirmed diagnosis of WHO grade 4 malignant glioma and radiographic evidence of recurrence or disease progression (as defined by the RANO criteria as a greater than 25% increase in the largest bi-dimensional product of enhancement or a new enhancing lesion, or a significant increase in T2/FLAIR abnormality without another co-morbid cause);
2. Age  $\geq$  18 years;
3. Karnofsky Performance Status  $\geq$  70%;
4. No more than 3 prior progressions;
5. Cohort 1 only: Non-bevacizumab failure, i.e. either no prior bevacizumab or bevacizumab stable/responder, which is defined as stable for at least 6 months from prior treatment with bevacizumab without experiencing a bevacizumab adverse event of special interest (AESI) while on a bevacizumab-containing regimen, such as:
  - a.  $\geq$  grade 3 hypertension not controlled by medication, hypertensive crisis, or hypertensive encephalopathy
  - b.  $\geq$  grade 3 proteinuria that does not resolve or nephrotic syndrome
  - c. Any grade GI perforation
  - d.  $\geq$  grade 3 infusion-related reaction
  - e.  $\geq$  grade 3 wound healing complications
  - f.  $\geq$  grade 3 hemorrhage or any grade CNS hemorrhage or  $\geq$  grade 2 hemoptysis
  - g. Any grade arterial thromboembolic event (e.g. myocardial infarction or cerebral infarction) or  $\geq$  grade 3 venous thromboembolic event
  - h. Any grade posterior reversible encephalopathy syndrome (PRES)
  - i.  $\geq$  grade 3 congestive heart failure
  - j.  $\geq$  grade 2 non-gastrointestinal (GI) abscesses and fistulae;
6. Cohort 2 only: Prior progression on a bevacizumab-containing regimen (defined as having progressed/grown through bevacizumab by RANO criteria within 2 months of prior bevacizumab treatment);
7. Pathology consistent with EGFR-amplification of tumor (i.e. greater than 15% of cells exhibiting  $> 5$  copies of EGFR loci); archival tissue may be tested for EGFR status in a separate consent;
8. ANC  $\geq$  1,000 cells/ $\mu$ l, platelets  $\geq$  100,000 cells/ $\mu$ l, hemoglobin  $\geq$  9 g/dL;
9. Adequate renal function as indicated by the following:
  - a. Serum creatinine  $\leq$  1.25 times upper limit of normal or calculated creatinine clearance  $\geq$  50 ml/min;

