  - b. Urine dipstick for proteinuria  $< 2+$  unless a 24-hour urine protein  $< 1$  g of protein is demonstrated;
10. Adequate liver function as indicated by the following:
  - a. Total bilirubin  $\leq$  1.6 mg/dL;
  - b. AST/ALT  $\leq$  2.5 x the ULN;
11. Magnesium  $\geq$  0.9 mg/dL;
12. For subjects on corticosteroids, they must be on a stable dose for *7 days* prior to anticipated start of study drug;
13. No evidence of  $>$  grade 1 active CNS hemorrhage on the baseline MRI or CT scan;
14. Signed informed consent approved by the Institutional Review Board prior to patient entry;
15. If the patient is a sexually active female of child bearing potential whose partner is male, or if the patient is a sexually active male whose partner is a female of child bearing potential, the patient must agree to use appropriate contraceptive measures for the duration of the treatment of the tumor and for 6 months afterwards as stated in the informed consent. Female patients of child bearing potential must have a negative serum pregnancy test within 48 hours of starting study treatment;

16. Fertile male subjects must agree to use a medically acceptable contraceptive method (allowed methods of birth control include vasectomy or condom with spermicide) during the trial and for a period of at least 6 months following the last administration of trial drugs.

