## 10 SCREENING AND ON-STUDY TESTS AND PROCEDURES

		Time Points								End of Treatment
		Cycle 1		Cycle 2		Cycle 3		Cycle 4...		
Evaluation	Screening a	Day 1	Day 15	Day 1	Day 15	Day 1	Day 15	Day 1	Day 15	
Informed consent	X									
Determination of EGFR amplification b	X									
History and complete physical exam, including full neurologic exam & KPS	X					X				X
Interval history and brief physical exam		X c	X	X	X		X	X	X	
Vital signs, including blood pressure and weight; calculate BMI d	X	X c	X	X	X	X	X	X	X	X
CBC with differential e	X		X	X	X	X	X	X	X	X
CMP + Mg e	X		X	X	X	X	X	X	X	X
Urinalysis	X									
Beta-HCG, if applicable, within 48 hours prior to start of study treatment, if contraception not initiated at time of negative test result prior to that time	X									
MRI of the brain f	X					X				X
Determination of EGFRvIII from archival tumor tissue g	X									
Quality of life measurements h	X					X				X
Skin toxicity assessment i	X		X	X	X	X	X	X	X	X
Toxicity assessment		Ongoing								
Pre-medication j		X								
Sym004 infusion		X	X	X	X	X	X	X	X	

a Within 2 weeks prior to first dose of Sym004. Some tests and procedures (as noted) are for a baseline only, not for eligibility.

b Determination of EGFR amplification may be taken from the original pathology diagnosis or maybe be tested from archival tissue as a part of screening by FISH (separate consent).

c Interval history with brief physical exam, vital signs, blood pressure, and weight do not need to be repeated if the screening exam and vitals occurred within 3 days of Day 1.

dBMI must be calculated before every infusion.

e Every 2 weeks, beginning with Cycle 1:Day 15.

f MRIs will be obtained every 8 weeks (i.e. every other cycle), prior to the start of the next cycle.

g EGFRvIII expression will be determined at baseline using archival tumor tissue; however, if a subject has more than one source of archival or frozen tissue, each source may be requested to determine if EGFRvIII expression has changed over time. EGFRvIII expression will be determined using IHC by the Duke Department of Pathology if not previously obtained.

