## 10.1 Screening Examination

If a candidate subject does not have EGFR status in his or her medical records, EGFR and EGFRvIII status may be tested from that patient's archival biopsy. The subject must sign a tissue screening consent before this can take place.

The screening examinations and procedures will take place within 2 weeks of starting study drug treatment. An informed consent must be signed by the patient before any research-related screening procedure takes place.

If screening occurs within 3 days of first study drug infusion, the screening tests can be used as Cycle 1 Day 1 examinations. Pre-treatment evaluations to determine eligibility are listed in the schema above and include the following:

- History and full physical exam, including a full neurologic assessment and KPS, two weeks prior to starting treatment
- Vital signs, including blood pressure and weight
- CBC with differential, CMP+Mg, Beta-HCG if appropriate (within 48 hours of beginning study drug if contraception not initiated at time of negative test result prior to that time)
- Urinalysis
- Baseline MRI of the brain 2 weeks prior to starting treatment
- Determination of EGFRvIII from archival tumor tissue
- Skin assessment, as a baseline measurement
- Quality of life measurements, as a baseline measurement
- Determination of EGFRvIII amplification

If a subject is found to be ineligible to participate in the study, minimal records regarding the subject and the reason for screen failure will be retained in the study database.

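### The schedule table and section 10.1 make the 48-hour pregnancy test conditional on contraception status, but inclusion criterion 15 requires it without exception

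*Combined protocol and SAP*

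**What the plan says.** Section 3.3, inclusion criterion 15, states the rule: "Female patients of child bearing potential must have a negative serum pregnancy test within 48 hours of starting study treatment". The heading above the inclusion list reads "answer must be YES to all criteria listed below", and section 9 refers the reader to 3.3 for the full set of criteria. Criterion 15 also asks sexually active patients to agree to contraception. It presents that as a separate requirement, not as a substitute for the test.

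The Beta-HCG row of the section 10 schedule also gives a 48-hour window but attaches a condition: "if contraception not initiated at time of negative test result prior to that time". The Beta-HCG item in 10.1 carries the same condition: "within 48 hours of beginning study drug if contraception not initiated at time of negative test result prior to that time".

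The screening window is two weeks. Footnote a of the schedule says "Within 2 weeks prior to first dose of Sym004", and 10.1 says "The screening examinations and procedures will take place within 2 weeks of starting study drug treatment".

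Section 10.9.6 mentions Beta-HCG once more, with the 48-hour window and without the contraception condition. It limits the test to patients for whom it applies, and it refers to Section 10 for the timing of laboratory tests.

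**The concern.** The same test has two rules. Under criterion 15, every woman of child bearing potential needs a negative result within 48 hours of the first dose. Under the schedule and 10.1, the natural reading is that a woman who started contraception at an earlier negative test need not be retested.

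Staff who work from the visit schedule could follow it exactly and still dose a patient who does not meet criterion 15. Pregnancy is exclusion criterion 1, and the 48-hour test is the last pregnancy check that the plan sets before first exposure. No laboratory test is scheduled on Cycle 1 Day 1, so no routine draw that day would reveal the omission. Once the patient has been dosed, the deviation stays in the trial: 13.1 analyses everyone who received any Sym004, and 10.8.3 replaces only patients who never started it.

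**Working it through.** The plan gives no figure to reproduce. The check sets the texts side by side and then bounds the age of the test.

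| Place | Who needs the 48-hour test | Exception |
|---|---|---|
| 3.3, criterion 15 | every woman of child bearing potential | none |
| Section 10, Beta-HCG row | as applicable | contraception begun at an earlier negative test |
| 10.1, Beta-HCG item | as appropriate | the same |
| 10.9.6 | as applicable | none stated; timing referred to Section 10 |

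**Test case.** A woman has a negative test on day -10, starts contraception that day and is not retested before her first dose.

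- Schedule row and 10.1: satisfied, because contraception began at the earlier negative test.
- Criterion 15: not satisfied, because the result is 10 × 24 = 240 hours old and the limit is 48.

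The two rules give opposite answers for her. They agree for a woman whose negative test falls in the last 48 hours, and for one who did not start contraception at an earlier negative test. The conflict is therefore confined to women who did start it then and whose test is more than 48 hours old.

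**Bound on the age of the test.** The inputs are the two-week screening window (footnote a and 10.1) and the 48-hour limit (criterion 15). The assumption is that the earlier negative test is the study's own screening test.

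- Oldest test the schedule accepts: 14 days × 24 = 336 hours.
- Excess over criterion 15: 336 − 48 = 288 hours = 12 days.

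Twelve days is a maximum, not an expected gap. The condition itself does not say how recent the earlier test must be. The 14-day bound comes only from the screening window.

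**The case against.** The strongest reply is that the condition is deliberate. It appears twice in almost the same words, and 10.1 gives the schedule an eligibility role of its own: "Pre-treatment evaluations to determine eligibility are listed in the schema above and include the following". On that view the sponsor meant to allow the exception, and criterion 15 is the text to amend. This stands in part. The documents do not show which rule was intended, and writing a time-limited exception into criterion 15 would also make them consistent. It does not remove the conflict, because criterion 15 as it stands contains no exception.

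A second reply is that the risk is slight. An affected woman still has an earlier negative test and has begun contraception, pregnancy remains an exclusion, and anyone checking the 3.3 list would meet the 48-hour rule. This also stands, and it keeps the point small.

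A reader might infer three stronger things that the documents do not support:

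- *That 3.3 formally overrides the schedule, so that the exception is unapproved.* No clause states which text prevails, and under 14.2 the protocol goes to the IRB with both texts in it. That 3.3 should prevail is a reasonable inference from its role as the complete eligibility list, but it is not a stated rule.
- *That 10.1 itself marks Beta-HCG as an eligibility test because it carries no baseline label.* Footnote a says "Some tests and procedures (as noted) are for a baseline only, not for eligibility", and in 10.1 the skin and quality-of-life items are labelled as baseline measurements while Beta-HCG is not. But EGFRvIII determination has no label there either, and it is in no eligibility criterion. A missing label proves nothing. Criterion 15 alone makes the test an eligibility item.
- *That pregnancy testing is waived altogether.* The condition relaxes only the 48-hour timing; an earlier negative result is still needed.

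**Conclusion.** The inconsistency is real in the current text, and no other section resolves it. A woman of child bearing potential who began contraception at an earlier negative test can be handled as the schedule and 10.1 say and still fail a mandatory inclusion criterion. If that test was the screening test, it may be up to 12 days older than criterion 15 permits.

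The conclusion rests on reading the conditional wording as a waiver of the 48-hour test, which is its only natural meaning. The 12-day figure rests in addition on the two-week screening window applying to the earlier test.

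The number of women affected cannot be derived from the documents and is probably small. The consequences are a possible eligibility deviation and a small safety risk. The PFS6 analysis, sample size and error rates are not affected. The correction is worth making because it is cheap and concerns exposure in pregnancy.

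**What to change.** Delete the contraception condition from the Beta-HCG row of the section 10 schedule and from the Beta-HCG item in 10.1. Both should then require a negative serum Beta-HCG within 48 hours before the first dose of Sym004 for every woman of child bearing potential, as criterion 15 does. Section 10.9.6 already gives 48 hours without the condition and needs no substantive change. The stricter rule is preferred because 3.3 is the complete eligibility list and because it is the safer of the two.

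The cost is a wording change in two places and at most one repeat blood draw in a few women whose screening test is more than 48 hours old. Criterion 15 already requires that draw. It may have to be a separate one, since no laboratory work is scheduled on Cycle 1 Day 1.

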**Exclusion Criteria (answer must be NO to all criteria listed below):**

1. Pregnancy or breastfeeding;
2. Prior treatment with EGFR-targeted therapy, including, but not limited to, the following examples: Gilotrif® (afatinib), Tarceva® (erlotinib), Erbitux® (cetuximab), Iressa™ (gefitinib), Vectibix® (panitumumab), Caprelsa® (vandetanib), Tykerb® (lapatinib), CDX110, D2C7-immunotoxin);
3. Active infection requiring intravenous antibiotics within 7 days before enrollment;
4. Prior, unrelated malignancy requiring current active treatment with the exception of cervical carcinoma in situ and adequately treated basal cell or squamous cell carcinoma of the skin;
5. Less than 12 weeks from radiation therapy, unless progressive disease outside of the radiation field or 2 progressive scans at least 4 weeks apart or histopathologic confirmation;
6. Treated with immunotherapeutic agents, vaccines, or Mab therapy within 4 weeks before enrollment, unless the patient has recovered from the expected toxic effects of such therapy;
7. Treated with alkylating agents within 4 weeks (6 weeks for nitrosoureas) before enrollment or treated within 1 week before enrollment with daily or metronomic chemotherapy, unless the patient has recovered from the expected toxic effects of such therapy to their baseline or to grade 1;
8. Prior treatment (non-alkylating agents) within 2 weeks before enrollment, unless the patient has recovered from the expected toxic effects of such therapy;
9. Known hypersensitivity reactions to any of the components of Sym004;
10. Known current drug abuse or alcohol abuse;
11. Known Human Immunodeficiency Virus (HIV), Hepatitis B, or Hepatitis C infection. Testing is not required as part of this study.

### **3.4 Data Analysis and Statistical Considerations**

Kaplan-Meier curves will be generated to describe the PFS and OS experience of patients enrolled on this protocol within each cohort and dose level. Progression-free survival (PFS) is defined as the time interval between initiation of protocol treatment and either disease progression or death. If the patient is alive and progression-free, PFS will be censored at the date last known alive. Overall survival (OS) is defined as the time interval between initiation of protocol treatment and death, or date of last follow-up if alive. Estimates with confidence intervals will be generated for median PFS and OS, as well as 2 month intervals for PFS for the first year (2, 4, 6, etc..) and 6 month intervals for OS for the first 2 years (6, 12, 18, 24) from the time the subject goes on study.

Radiographic response rate will be estimated as the proportion of treated patients with a complete or partial response (see Appendix B). An exact binomial confidence interval will be generated.

[figure not shown]
For each type of toxicity, the maximum grade experienced by each patient will be summarized with frequency distributions within each cohort and dose level. Two adverse experience tabulations will be generated, one that includes all toxicities regardless of attribution, and one that includes only toxicities that are possibly, probably, and definitely related to Sym004 treatment.

Cox proportional hazards model will be used to examine the association between EGFRvIII expression and PFS and OS.

At the 18 mg/kg dose level, interim analyses will be conducted after 19 total patients across both cohorts have been treated with Sym004. These interim analyses will focus on the prevalence of skin toxicities.

With each cohort of the study at the 24 mg/kg dose level, the study is designed as a two-stage study to assess 6-month PFS. After the initial stage, interim futility analyses will be conducted.

## 4 STUDY SCHEMA

## 5 BACKGROUND AND SIGNIFICANCE

### 5.1 Study Disease

There is an unmet clinical need for the therapy of malignant gliomas with a median survival of <20 months despite available therapies. The current standard of care is radiation therapy with daily temozolomide followed by 6 cycles of temozolomide.

Glioblastoma (GBM) is a highly angiogenic, aggressive malignant primary brain cancer; it is the most common and aggressive type of primary brain tumor in humans. It accounts for 52% of all primary brain tumor cases and 20% of all intracranial tumors. The median progression-free survival for patients treated with surgery followed by radiation and temozolomide is under 7 months. Median overall survival is under 15 months. No effective therapy exists following recurrence. Few cytotoxic drugs are available for the treatment of GBM because of the difficulty of crossing the blood-brain barrier. Temozolomide, an alkylating agent, is the current standard of care in combination with surgical resection and radiation therapy. Recurrent GBM has an initial response to temozolomide therapy. Although different dosing regimens have been tried to reduce the tumor burden, GBM loses sensitivity to temozolomide. Overall survival is not improved and tumor progression results. Effective treatment remains an unmet medical need.

### 5.2 Study Agent

Sym004 is a recombinant antibody mixture that binds specifically to the epidermal growth factor receptor (EGFR). Sym004 contains two mouse-human chimeric IgG1 monoclonal antibodies, futuximab and modotuximab, in a 1:1 ratio. Per the Investigator's Brochure (v. 2.0, 22-Jan-2015), the antibodies bind to non-overlapping epitopes on the extracellular domain III of EGFR. The binding induces a distinct mechanism of action that is dependent on the presence of both antibodies and translates into a superior anti-cancer activity compared to monoclonal reference antibodies. This was demonstrated both *in vitro* using human cancer cell lines and *in vivo* using EGFR-dependent tumor xenografts. Sym004 induces highly efficient internalization of EGFR on cancer cells and degradation, which results in inhibition of cancer cell growth. Sym004 is being investigated for the treatment of subjects with advanced metastatic colorectal cancer (mCRC), for the treatment of recurrent or metastatic squamous cell carcinoma of head and neck (SCCHN), for the treatment of non-small cell lung cancer (NSCLC), and for the treatment of esophageal squamous cell carcinoma (ESCC) in Japanese subjects.

Studies have shown that Sym004 is superior at inhibiting EGFR activity compared to cetuximab and/or panitumumab (used as reference antibodies) *in vitro* through a mechanism of action that is dependent on binding of both antibodies. Furthermore, the activity of Sym004 was investigated in several xenograft tumor models in mice and compared to cetuximab and/or panitumumab. In all models, Sym004 was superior or as efficient as these reference antibodies.

Five clinical trials have been completed with Sym004 and 2 clinical trials are currently ongoing according to the most recent Symphogen Development Safety Update Report (report dated 13 Mar 2017). Sym004 shows early signs of promising activity in the trials conducted so far. Sym004 was shown to induce tumor shrinkage in subjects resistant to combination treatment with platinum-based chemotherapy and cetuximab in recurrent/metastatic SCCHN. The median OS with Sym004 of around 5 months is in the range of the reported median OS in less heavily pre-treated (cetuximab-naïve), platinum-resistant recurrent/metastatic SCCHN subjects treated with compounds such as methotrexate or cetuximab. In subjects with mCRC and acquired resistance to cetuximab, Sym004 showed promising activity as it was able to induce tumor shrinkage in about 30-48% of subjects including several cases of partial response.

### 5.3 Study Purpose/Rationale

Glioblastomas (GBMs) are highly aggressive and lethal malignant brain tumors. The human epidermal growth factor receptor (EGFR; HER-1) is a transmembrane receptor tyrosine kinase. It is an attractive therapeutic target

for based on its role as an oncogenic driver. EGFR is amplified in 35-40% of primary GBM tumors. Approximately 50% of EGFR-amplified GBMs express EGFRvIII, a constitutively active, ligand-independent mutant receptor with impaired down-regulation. So far, most efforts at targeting EGFR have revolved around the utilization of tyrosine kinase inhibitors, which have almost invariably failed to show efficacy in WHO grade IV malignant glioma patients.

Sym004 is a recombinant antibody mixture which binds specifically to EGFR. Sym004 contains 2 mouse-human chimeric IgG1 monoclonal antibodies (Mabs), futuximab and modotuximab. The antibodies bind to non-overlapping epitopes on the extracellular domain III of EGFR. Sym004 is not only designed to block ligand binding, receptor activation and downstream signaling but also elicits effective removal of the EGFR receptors from the cancer cell surface by inducing EGFR internalization and degradation. In addition, unlike the single monoclonal anti-EGFR antibodies which only mediate antibody-dependent cellular cytotoxicity (ADCC), Sym004 mediates both ADCC and complement-mediated cytotoxicity against EGFR-positive tumor targets. The activity of Sym004 was investigated in several xenograft tumor models in mice and compared to cetuximab and/or panitumumab. In all models, Sym004 was either superior to or as efficient as these reference antibodies. Three clinical trials have been completed with Sym004 as a single agent in subjects with recurrent advanced solid tumors (Sym004-01, Sym004-02, and Sym004-06). Sym004 shows signs of promising activity in both trials conducted so far. Skin toxicities were the most frequently reported AEs, seen in 80-97% of subjects.

Given the dire need for new therapies for recurrent GBM, particularly after bevacizumab-failure, the proposed clinical trial is an important step in the field of neuro-oncology. To assure that the appropriate patient population will be enrolled on study, only recurrent WHO grade IV malignant glioma patients with known EGFR amplification as defined in the eligibility criteria (at diagnosis or at recurrence) will be eligible.

